7.1.8 Subgroups

No subgroup analyses will be performed.

7.2 Analysis Sets

The decision on the classification of subjects to each analysis set will be taken at the clean file meeting, prior to breaking the blind, and documented in the clean file report together with the reasons for excluding subjects from analysis sets. Subjects who have not attended any visits where disease status is assessed, i.e. those who did not reach the day 30 visit, the first visit where disease status is recorded, will be classified as dropouts from the efficacy analysis sets. Any 30dayFU visit that is under the window, i.e. visit occurred too soon, will not be removed from the analysis population as long as the 90DayFU visit also proved that the patient was cured.

LINK Medical Study ID: PSR012

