- 3. If within 90 days after end-of-treatment and within 11 months (Day 335) after randomization the subject relapses, and cultures are negative for *Acanthamoeba*, treatment with the study drug will be re-started according to the treatment schedule, starting with the Day 0 treatment regime. Assessments and visits will also be restarted at Day 0, Day 30 and all consecutive visits of the treatment phase. A detailed treatment plan and follow-up protocol is provided in Section 5.3.
- 4. End-of-study is defined as: (a) the last follow-up visit at 90 days after end of treatment, (b) the day of study drug unmasking in the event of the subject becoming a Treatment failure, (c) if withdrawn from the trial of other reasons, (d) if a subject has been treated for 12 months after randomization (also a Treatment failure).
- 5. Screening and baseline assessments will take place on Day -2 to 0, before randomization and study drug administration.
- 6. For subjects who have not reached the age of majority (i.e. 18 years of age in most jurisdictions), the subject must provide assent (written or verbal) and the parent/guardian/legally authorized representative must provide written informed consent before the subject's participation in the study.
- 7. All medical and medication history related to the current eye infection will be reported. For the remaining medical and medication history, only the last 30 days before signing the ICF will be reported in the case report form (CRF).
- 8. Confocal microscopy is optional if already performed within 7 days prior to study entry as part of standard care providing the images are available to the Investigator to assess.

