5.3. Treatment and Follow-up Protocol

A schematic overview of the treatment and follow-up period is presented in figure 2.

[figure not shown]

Figure 2: Schematic Presentation of the Treatment and Follow-up Protocol

Legend for Figure 2 - The text boxes and lines in the figure are color coded:

- Pale blue text boxes and lines for responding disease or treatment success and STUDY END POINT
- Red text boxes and lines for poorly responsive and recurrent / relapsing disease presumed to be due to replication of *Acanthamoeba*
- Pink text box for exacerbations of inflammation presumed to be due to flare ups of inflammation secondary to the immune response to non-viable *Acanthamoeba*
- Black text boxes for treatment failure endpoints ALL leading to TRIAL EXIT

This protocol defines the treatment of patients. Treatment options are defined as far as possible to reduce variations, which will complicate or invalidate the analysis of the results, whilst maintaining optimal standards of care based on current evidence and expert opinion. The changes of therapy in this protocol, and therapeutic failures, are determined by both the development and resolution of clinical signs of inflammation and ulceration, as well as the identification of *Acanthamoeba* by culture during disease relapses.

Each box is labelled with a Roman numeral I to XVIII. The legend below describes the rationale for each step:

BOX I. FOLLOW UP PROTOCOL from day zero at TRIAL ENTRY.

Treatment throughout the study is given using 1 drop of each ophthalmic solution in the study eye at different frequencies during the daytime only.

At study entry initiate an intensive 19-day antiamoebic treatment protocol:

Day 0 to 5

1-hourly drops (16 drops in a day) for 5 days

Day 6 to 12

2-hourly drops (8 drops in a day) for 7 days

Day 13 to 19

3-hourly drops (6 drops in a day) for 7 days

Day 20

then 4x daily thereafter

- a. This frequency is maintained at 4x daily unless a relapse (BOX XI RELAPSE) occurs. In case of a relapse, culture negative subjects receive the same intensive 19-day treatment course as given at study entry.
- b. Antiamoebic drops are discontinued when IV DISCONTINUE TREATMENT is reached.

In subjects on steroids at TRIAL ENTRY: (already using topical steroids for e.g. mistaken diagnosis of HSV keratitis or as adjunctive treatment for bacterial keratitis), the same intensive 19-day antiamoebic treatment protocol is used. For their steroid use there are these options:

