5.3.3. Relapse

BOX XI RELAPSE WITHIN 11 MONTHS

Relapse within 11 months, after an initial response is common. Cultures for *Acanthamoeba* and other organisms (fungi, bacteria and herpes) must be repeated, deriving from a repeated corneal biopsy, if the investigator thinks this is appropriate.

- c. If the CULTURES are NEGATIVE patients this may mean that the anti-amoebic therapy is having some effect although we have no way of being certain about this (confocal and PCR don't help as these can be positive when the organisms are non-viable). These patients are managed as described in XIII below with another 19 day course of intensive therapy, with or without anti-inflammatory therapy depending on status.
- d. If CULTURES are POSITIVE patients have TREATMENT FAILURE and managed as described in XIV and XVII below.

Box XII. EXACERBATION of inflammation is presumed to be due to inflammation secondary to the immune response to non-viable Acanthamoeba and anti-inflammatory treatment can be re-started or increased at the discretion of the PI without the need for re-culture and a further course of intensive anti-amoebic therapy. IMPORTANT: if anti-amoebic treatment had been stopped restart this when anti-inflammatory treatment is re-started.

Distinguishing between XI and XII is often difficult and guidelines for this are given in II a, b above.

Box XIII. Restart with another 19 day intensive course of anti-amoebic therapy with or without topical steroids and oral NSAIDS:

- a. If patients were not on these at the time of the relapse of infection we recommend not using these until after the 19 day course of intensive treatment and depending on response move to as above.
- b. If they were on them at the time of the relapse continue at a dose determined by the PI and follow pathways II, III, IX or X.

Box XIV. CULTURE POSITIVE these patients are Exit Trial and are managed as described in XVII below.

Box XV. SCLERITIS UNRESPONSIVE to treatment in IX. This is a failure (see XVII below).

Box XVI. RELAPSE after day 335 or ingoing inflammation and treatment at day 365: this is a treatment failure and is managed as described in XVII below

Box XVII. TREATMENT FAILURE and EXIT TRIAL. The treatment randomization allocation will be opened by the Sponsor at this point. Trial drug (PHMB 0.08%) will be available to the patient, if requested by the Investigator, providing the patient continues trial follow up for safety evaluation.

XVIII. Summary of Study end points.

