5.6. Masking

This study is designed as double-masked, double-dummy study. However, the bottle of the dummy (placebo), although very similar, is not identical to the bottle of the study product, as it was not possible to obtain an identical bottle. Because unmasking is allowed per protocol in case of lack of efficacy, there is a small risk of disclosing of the treatment assignment for subjects continuing to participate in the study. To reduce this risk, and to protect the integrity of the data, efficacy assessments should be performed by study personnel not having access to the study treatment, dispensing logs, accountability forms, the eCRF, or other sources of treatment assignment information (assessor-masked design). In particular the records of unmasked subjects should not be seen by the doctors carrying out the study. The investigator and other study staff, the subjects, the monitors and the sponsor will only have access to masked treatment assignment information on a 'need to know basis' until data collection has been completed, the database is locked and the protocol deviations and the primary reason for discontinuation from the study for each subject are determined. The exact requirements and process will be outlined in the Study Operations Manual.

The randomization code does not disclose any treatment information. Until the moment of unmasking, the treatment assignments linked to the codes are accessible only by the individuals appointed by the Sponsor as Qualified Persons responsible for Pharmacovigilance. Emergency Unmasking should only be done if knowledge of treatment assignment is considered relevant for medical care of the patient. Unmasking is an Investigator's responsibility and, if in doubt, can be discussed with the Medical Monitor. Details will be provided in the Study Operations Manual.

Subjects will be treated for a maximum of 1 year after randomization. Study treatment may be unmasked for serious safety reasons. These unmasked subjects will be discontinued from the study

The randomization code will be broken when all subjects have finished the study.

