7.2.2 Per-Protocol Analysis Set (PPAS)

The per-protocol analysis set is defined as the subset of subjects in the FAS for whom no major protocol deviation judged as having an impact on the primary efficacy analysis was reported or identified. The last disease status assessment within 12 months of randomisation will be used for disease status assessment. For subjects with disease resolution at that last visit, the 30-day and 90-day follow-up assessments should confirm disease resolution. Otherwise, the disease will be regarded as not having been resolved.

The decision as to which protocol deviations should be considered as reason for exclusion from the PPAS should be made at the clean file meeting and documented in the clean file report.

Analysis on the PPAS will be based on the actual treatment (i.e. subjects will be analysed 'as treated'). The primary efficacy variable, CRR_12, will also be evaluated using the PPAS.

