where ORRES BCA1 and ORRES_BCA2 are the annotated values from the BCVA test. These values are positive number with up to one decimal value. ORRES BCA1 values recorded in the eCRF, the distance from the subject to the chart, varies at least from 0.6 to 10 metres. Even if different scales are used (Decimal, US, 6m), the LogMAR is not affected since the ratio will be the same, therefore no converting to unified units is needed². BCV A, as a secondary efficacy variable, will be analysed. ANCOVA will be used with treatment and the Baseline value of LogMAR as predictors. Refraction at Baseline may also be used as a predictor.

Drug compliance

Drug compliance is recorded as Yes or No answer to the question "Was the study drug administration compliant with the protocol?", annotated as PROTCOMYN. Drug compliance will be analysed with a logistic regression model and model-based estimates of the difference between treatments, odds ratio with corresponding CIs and p-values will be provided. Covariate variables such as treatment, age and sex will be included. Any available information regarding drug use will also be presented, such as number of vials returned.

EQ-5D-5L3 & EQ VAS, at all visits

EQ-5D-5L consists of 5 dimensions, Mobility, Self-care, Usual activities, Pain/discomfort, and Anxiety/depression, each answered with one of five different answers:

Mobility:

I have No problems/Slight problems/Moderate problems/Severe problems in walking about/I am unable to walk about

³ One subject, aged 15 years, used the EQ-5D-Y version. At site 31, Silesia, all subjects at one or more visits used the EQ-5D-3L version

Transaction 09222115557449620377 Signed CE, VP, MS

¹ For safety variables, see Section 7.10.2

² RR.2 Reference Tables For Equivalent Visual Acuity Notations

LINK Medical Study ID: PSR012

Self-care:

I have No problems/Slight problems/Moderate problems/Severe problems in washing or dressing myself/I am unable to wash or dress myself

Usual activities (e.g. work, study, housework, family or leisure activities):

I have No problems/Slight problems/Moderate problems/Severe problems doing my usual activities/I am unable to do my usual activities

Pain/discomfort:

I have No pain or discomfort/Slight pain or discomfort /Moderate pain or discomfort /Severe pain or discomfort/I have extreme pain or discomfort

Anxiety/depression:

I am not/slightly/moderately/severely/extremely anxious or depressed.

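### Analysis sets are to be settled while masked, but the sponsor opens each treatment failure's allocation at exit and nothing keeps those who then know it out of the decisions

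*SAP*

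**What the plan says.** **When the sets are decided.** SAP 7.2: "The decision on the classification of subjects to each analysis set will be taken at the clean file meeting, prior to breaking the blind". SAP 7.2.2 adds: "The decision as to which protocol deviations should be considered as reason for exclusion from the PPAS should be made at the clean file meeting". Protocol 7.1.1 had promised that the SAP would contain the PPAS criteria. SAP 7.2.1 also makes a confirmed diagnosis a condition for the FAS. Protocol 7.1.1 does not have this condition, and the SAP does not define it.

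**When allocations are opened.** Protocol 5.3.3, Box XVII, says of a treatment failure: "The treatment randomization allocation will be opened by the Sponsor at this point". The legend in Protocol 5.3 reads: "Black text boxes for treatment failure endpoints ALL leading to TRIAL EXIT". Note 4 to the Schedule of Assessments counts as end of study "the day of study drug unmasking in the event of the subject becoming a Treatment failure". Protocol 5.6 acknowledges the practice ("Because unmasking is allowed per protocol in case of lack of efficacy") and later says: "The randomization code will be broken when all subjects have finished the study".

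**What protects the masking.** Under Protocol 5.6 the codes stay with sponsor-appointed pharmacovigilance persons until unmasking. Sponsor, sites and monitors have need-to-know access until the database is locked and deviations are determined. Study doctors should not see the records of unmasked subjects. SAP 5.2 says early unblinding will be accounted for before the code break and gives no method.

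**The concern.** The statement in SAP 7.2 is true of the overall code break. For treatment failures, the sponsor has by then opened the allocation as a matter of routine. Those subjects almost always count against their arm, so arm and outcome can both be known for them, while cured subjects stay masked.

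The clean file meeting still has room for judgement. It chooses which deviations exclude a subject from the PPAS and applies the undefined diagnosis condition to the FAS. SAP 7.9.1 makes similar FAS and PPAS results a condition for non-inferiority, so both sets bear on the conclusion. If someone in the room knows opened allocations, the trial cannot show afterwards that the sets were chosen masked.

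**Working it through.** **1. Order of events.** A subject fails and exits, and the sponsor opens the allocation (Box XVII). Later, after data cleaning, the clean file meeting classifies subjects (SAP 7.2). The overall code break follows (Protocol 5.6, SAP 5.2). Opening at failure thus comes before classification. The documents do not say who receives an opened allocation, who attends the meeting, or that the two groups must be separate.

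**2. Where judgement enters.**
- PPAS: SAP 7.4 lists two major deviations, not complying with allocated treatment and not attending the two follow-up visits. Protocol 5.2 adds non-compliance by missed days. The rest is left to the meeting. A subject who exits as a failure during treatment does not reach the follow-up visits, so the second deviation, read literally, can apply to failures because they failed.
- FAS: SAP 8.2 tabulates diagnosis by confocal microscopy alone or with culture, PCR or both. Protocol 6.1.2 sends images to a central reader but accepts the investigator's reading for entry. The SAP does not say which of these confirms a diagnosis.

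**3. The plan's own figure.** Inputs from Protocol 7.6: 63% v 83%, two-sided alpha 0.10, power 80%, 10% loss. With unpooled variance,

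n = (1.645 + 0.842)² × (0.63×0.37 + 0.83×0.17) / 0.20² = 6.183 × 0.3742 / 0.04 = 57.8.

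That is 58 per arm, or 116 evaluable. Then 58/0.9 = 64.4, so 65 per arm and 130 in total. Both match the plan.

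**4. How many allocations could be open.** Expected non-cures per arm are n(1 − p), with n = 58:
- Design case: 58×0.37 + 58×0.17 = 21.5 + 9.9 = 31.3, and 31.3/116 = 27%.
- Both arms at 63%: 2 × 21.5 = 42.9, and 42.9/116 = 37%.

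These are upper bounds. SAP 7.9.1 also counts discontinued subjects as not cured, and those who leave for other reasons are not routinely opened.

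**5. How few FAS exclusions matter.** The cure counts are assumed for illustration. The lower 90% limit is d − 1.645 × √(p₁q₁/n₁ + p₂q₂/n₂), test minus control, with test-arm failures removed.

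| Test v control | Removed | d | SE | Lower limit |
|---|---|---|---|---|
| 33/58 v 37/58 | 0 | -0.069 | 0.0906 | -0.218 |
| 33/56 v 37/58 | 2 | -0.049 | 0.0911 | -0.199 |
| 43/58 v 37/58 | 0 | 0.103 | 0.0854 | -0.037 |
| 43/55 v 37/58 | 3 | 0.144 | 0.0842 | +0.005 |

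The linear model in SAP 7.9.1 (pooled variance, t quantile) gives slightly wider limits. The first case goes from -0.221 to -0.201 after two removals and -0.191 after three. The second goes from -0.039 to +0.002 after three.

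A single exclusion can also suffice. With 65 per arm and the linear model, 37/65 v 41/65 gives -0.0615 − 1.657 × 0.0864 = -0.205, and 37/64 v 41/65 gives -0.0526 − 1.657 × 0.0866 = -0.196.

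**The case against.** The strongest reply is that the plan is not silent. Protocol 5.6 restricts treatment information until deviations and discontinuation reasons are determined, which covers the decisions at issue. Codes sit with pharmacovigilance, early unblinding must be accounted for, and details may be in the Study Operations Manual, which is not among the documents. The sentence on breaking the code is naturally read as the overall break. This reply stands in part: safeguards exist. But need-to-know access names nobody who is barred, and pharmacovigilance custody is stated only until unmasking.

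Four stronger readings are tempting and not supported:
- A reader might infer that the set decisions are in fact made unmasked. No text says meeting members see allocations.
- A reader might infer that the opened subjects are exactly those who count against an arm. Other discontinued subjects also count as not cured.
- A reader might infer that PPAS discretion can move the primary estimate. It cannot: SAP 7.9 makes the FAS the basis and the PPAS supportive. If the FAS misses the margin, PPAS exclusions do not rescue it. They can only affect whether the two sets agree.
- A reader might take SAP footnotes such as "One subject, aged 15 years, used the EQ-5D-Y version" as evidence of compromised masking. They show that collected data had been looked at, but reveal neither arm nor outcome.

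The numerical examples are also fragile. With control at 41/65, 37 is the only test-arm count at which one exclusion crosses -0.20. If the 95% interval also named in SAP 7.9.1 is taken as two-sided, the limits are -0.233 and -0.224, with no crossing.

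**Conclusion.** The point holds as a gap in protection. By the clean file meeting the sponsor may know the arm of up to about 31 of 116 evaluable subjects (27%) under the design assumption, or about 43 (37%) if both arms cure 63%. Both figures assume that every non-cure is an opened treatment failure. Nothing in the two documents keeps people with that knowledge away from PPAS exclusions or the FAS diagnosis condition. In a borderline result, one to three FAS exclusions could move the lower 90% limit across -0.20 or 0, on assumed counts. No biased decision is shown or implied. The case for acting is that masked set selection has to be demonstrable, and for treatment failures the current text does not make it so.

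**What to change.** 1. State in SAP 7.2 that everyone who prepares listings for, attends or signs the clean file meeting has had no access to any opened allocation, or to post-exit treatment data that would reveal one. Pharmacovigilance keeps the access log.
2. Before the meeting, complete in the SAP the list of deviations that exclude a subject from the PPAS, and define the confirmed diagnosis required for the FAS. State that missing follow-up visits because of protocol-defined treatment failure is not an excluding deviation.
3. Reconcile Protocol 5.3.3 (Box XVII) and 5.6 with SAP 5.2 and 7.2, so that opening one subject's allocation at failure is distinguished from the overall code break and its recipients are named.
4. Report the primary result in all randomized subjects as a sensitivity analysis.

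The protection should rest on who takes part. Listings stripped of exit reason and outcome would not work, because SAP 7.2, 7.2.1 and 7.4 need that information to apply their own rules.

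The cost is wording in the SAP and protocol, an access log and one additional analysis. The downside is that sponsor staff who know opened allocations cannot take part in the meeting.
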